## Data Analysis and Statistical Considerations

**Power Analysis:** We propose randomizing 130 participants per condition (N = 260). Given this sample size, power was evaluated under a range of assumptions including a 15% loss to follow-up or 110 participants per condition (although under the ITT principle all 130 participants will be included in the analysis). Attrition in our pilot ([name], [name], Johnson et al., in press) at 8 weeks was 10%, similar to the 15% rate of a VA multi-site RCT with VA primary care patients. Attrition will be minimized by allowing intervention and follow-up sessions to be by phone and offering flexible scheduling of assessments (e.g., evening/ weekend times). The proposed sample size provides 80% power to detect a meaningful between group effect corresponding to a CAPS-5 difference of 7-15 points (or a Cohen's  $d$  of 0.4 or greater). These calculations conservatively assume a CAPS-5 SD ranging from 16-20 and a two-sided Wald test conducted with an alpha of .05. The effect size needed to detect a meaningful difference (i.e.,  $d = .4$ ) is smaller than what we found in our pilot work (i.e.,  $d = .55$ ). Equally important, this sample size provides adequate power to detect a statistical difference between conditions on percentages achieving clinically significant outcomes (i.e., can detect a 20% minimal difference, which is smaller than what our pilot data demonstrated, i.e., a 50% difference).

**Data Analysis:** The main goal of Aim 1 is to determine the effect of CS PTSD Coach on PTSD symptoms. More specifically, we will measure the impact of CS PTSD Coach on change in CAPS-5 score at 8 weeks. Mixed effects linear regression will be used to determine whether the effect of CS PTSD Coach on change in CAPS-5 score at 8 weeks is different from that of the comparison condition (i.e., PC-MHI TAU). As all participants will have a baseline score, they all will be included in the model, adhering to the ITT principle. The mixed effects model will include a subject-specific random effect to account for the correlation of CAPS-5 score within a person over time. Finally, because randomization is stratified by site, site will be included as a fixed effect in our model.

The objective of Aim 2 is to correlate treatment arm with engagement in specialty MH care. We will evaluate the effect of the CS PTSD Coach condition on rate of attendance to at least 2 specialty MH visits post randomization (week 1 to week 24). To evaluate whether rates of attendance differ by condition, we will fit a mixed effects logistic regression model with a subject-specific random effect, an indicator for condition, and indicators for each time point. We are particularly interested in the effect of condition at 24 weeks. The parameter of interest, therefore, is the interaction term that corresponds to rate of treatment attendance at 24 weeks.

Several approaches will be used to evaluate our Exploratory Aims. To explore potential mediators (i.e., amount of app use, improvement in coping self-efficacy), we will fit 2 models for each potential mediator. One will include condition only and the second will include condition and the potential mediator. Change in the coefficient corresponding to condition after inclusion of the mediator may indicate a mechanism of action. To examine possible moderators (e.g., baseline PTSD severity), interaction terms between possible moderators and condition will be assessed. Significant interaction terms will suggest that the effect of intervention varies by

levels of the moderator. Lastly, to evaluate symptom trajectories over time, we will consider a mixed effects model of PCL scores at all time points with indicators for each follow-up visit (at 8, 16, and 24 weeks), randomization group, and an interaction between the indicators for time and condition as represented by the 3 product terms. A test evaluating all 3 product terms will address whether CS PTSD Coach affects the overall trajectory of PCL score. We will also explore if trajectories are moderated by continued PTSD Coach use and receipt of MH treatment. A similar approach proposed to test Aim 1 will be used to determine if CS PTSD Coach has broader effects, beyond PTSD symptom improvement, on depression and quality of life.

**Qualitative Analyses:** For Aim 3, a team-based approach will be used to analyze the patients' interview data following a qualitative descriptive study approach. The team will engage in a two-stage process for analysis: top-level coding and sub-coding. The team will first review several interview transcripts to identify a provisional list of broad initial top-level codes that reflect key concepts from the interview schedule (e.g., intervention utility/usefulness, strengths, weaknesses). A codebook will be developed that will contain code names, definitions, rules for code assignment, and text exemplars. Following agreement on the initial top-level code definitions, team members will independently begin applying top-level codes to the transcribed interviews. To ensure accuracy and consistency of coding, the full team will meet weekly to discuss findings, resolve inconsistencies, and reach consensus throughout the coding process. We anticipate that top-level codes will be very broad and will develop sub-codes for a more descriptive analysis using an inductive approach to identify emergent concepts. For example, sub-codes for the top-level category "intervention utility" may be "distress management" or "social connectedness". To finalize the analysis, team members will all code to reach consensus on the interpretation of the patterns within and across codes to suggest themes. ATLAS.ti software will be used to manage data and facilitate analysis across multiple coders. Interviewing a random sample of 30 participants in the CS PTSD Coach arm of the trial will provide ample text data to identify themes regarding patient satisfaction and suggestions for future modification to CS PTSD Coach. Although there will be insufficient provider interviews (n = 4) for a detailed qualitative analysis, the analytic team will collectively review transcripts to search for consistencies in key strengths and weaknesses of the intervention.

**Missing Data:** Based on previous studies with similar samples and study procedures conducted by the PIs, we estimate a 15% attrition rate at post-treatment. We will fully describe all missing data at each time point. In addition we will characterize any patterns of missing data where possible (e.g., we will describe whether those missing a PCL score at any time point are older on average). Our primary analytic approach relies on a flexible assumption that the data are "missing at random" (MAR) or that missingness may be systematically related to observed features only

**Analytic Sets:** In sensitivity analyses, we will assess the robustness of our findings to the MAR assumption by incorporating multiple imputation-based tools into our regression models that assume data are not missing at random as well as alternative models under the missing at random assumption.

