**Continuing Review Form**

**1. Participant Enrollment**

- a. Number of participants entered (or number of specimens examined or charts reviewed) since the beginning of study. If this is a combined VA-Stanford study, in addition indicate how many of the participants (or number of VA specimens examined or VA charts reviewed) enrolled with a VA consent. If this is a multi-site study, in addition to the number of participants enrolled locally, include the number of participants enrolled study-wide.**

At the VA Palo Alto HCS, we have enrolled 122 participants since the beginning of the study on May 1, 2017. Of these, 70 were eligible for randomization to study treatment conditions.

At the collaborating site, the VA Syracuse, 234 participants have been enrolled since they began recruitment on February 1, 2017. Of these, 164 were eligible for randomization to study treatment conditions.

\*The original N for the entire study (i.e., across both sites) proposed for randomization to study conditions was 260. As is reflected in our DSMB report for 2019 (attached in Section 16) we reconsidered statistical power given that we had sufficient data to update assumptions we used to originally calculate power and the resultant sample size required to achieve it in the proposal. The original assumption of the standard deviation for the CAPS-5 (i.e., our primary outcome measure) was much higher (i.e., 16) than what we found in the data we had collected to date (i.e., SD = ~11). Therefore, we used this empirically-derived figure to recalculate power and the minimum required sample size needed to achieve it. Based on this, we needed to randomize at least 95 participants per condition instead of the originally proposed 130 per condition. We ultimately were able to randomize 114 to CS PTSD Coach and 118 to TAU, which will provide sufficient power to test our primary as well as our secondary outcomes.

- b. Number of: males, females, others or individuals whose sex/gender are unknown or not reported.**

Of the 122 enrolled at Palo Alto:  
Number of Females= 7  
Number of Males= 115

- c. Minority status of participants entered since beginning of study.**

29 African American/Black  
16 Asian/Pacific American  
5 Native American/Indian  
10 Hispanic  
17 Others  
(55 Caucasian/White)  
\*Categories not mutually exclusive

- d. Number of children (less than 18 years) entered since beginning of study.**

N/A

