**b. Number of participants lost to follow-up since the beginning of the study.**

There are 11 participant lost to follow-up since the beginning of the study.

**c. State if all adverse events have occurred at the expected frequency and level of severity as per study documents or provide a narrative summary of the adverse events since the last continuing review indicating whether the adverse events were expected and/or related to the study.**

No adverse events were experienced by participants at our site (i.e., the VA Palo Alto). At the collaborating site, the VA Syracuse, 5 adverse events were reported (through February 2018) with all being deemed to be unrelated to study participation (please see section 16 for the most recently submitted DSMB report (for 2020)for details).

**d. Have there been any unanticipated problems involving risks to participants or others (UPs) since the beginning of the study? A UP must be unexpected (including in severity or frequency), related, AND harmful. Confirm that all UPs have previously been reported to the IRB (guidance GUI-P13).**

No unanticipated problems involving risks to participants or others have occurred in the past year.

**e. Provide a narrative summary of all external (e.g. FDA, OHRP, sponsor) audit reports, monitoring visits, inspections, and multi-center trial reports received in the past year. Include corrective actions taken as a result of any audits, inspections, or monitoring visits.**

No reports were received in the past year.

A consent audit was completed on October 11, 2019 with 94 informed consent documents and HIPAA authorization forms reviewed by the VA Research Compliance Office. No reportable findings were found in that audit.

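### The SAP's 7–15 point range at 80% power does not match its own inputs: for the main comparison they give about 6.0–7.6 points with 110 per arm, and 15 is not a detection limit

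*SAP*

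**What the plan says.** All the planning inputs are in the Power Analysis paragraph of the SAP.

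- Sample size: "We propose randomizing 130 participants per condition (N = 260").
- Attrition: "power was evaluated under a range of assumptions including a 15% loss to follow-up or 110 participants per condition". The same sentence adds that all 130 per arm stay in the intention-to-treat analysis.
- Claim: "80% power to detect a meaningful between group effect corresponding to a CAPS-5 difference of 7-15 points", which the sentence equates with a Cohen's d of 0.4 or more.
- Assumptions: "These calculations conservatively assume a CAPS-5 SD ranging from 16-20 and a two-sided Wald test conducted with an alpha of .05".

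The paragraph gives no derivation or source for 7 or for 15. It does not say whether the SD is that of a score at one visit or of a change score, and it gives no correlation between baseline and week 8. The Aim 1 analysis is of change: "we will measure the impact of CS PTSD Coach on change in CAPS-5 score at 8 weeks".

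The Continuing Review Form in the protocol (item 1, Participant Enrollment) later replaces these inputs. It contrasts the assumed SD of 16 with "what we found in the data we had collected to date (i.e., SD = ~11"), and reports: "We ultimately were able to randomize 114 to CS PTSD Coach and 118 to TAU". It does not say which SD the 11 is.

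**The concern.** The sentence gives the same effect in points and in SD units, and the two do not agree. At SD 16–20, 15 points is d = 0.75–0.94, far from 0.4. A reader who takes 7–15 as the detection limit would think that a true difference of up to 15 points had a one-in-five chance of being missed. That reader would then interpret a null or small CAPS-5 result against the wrong yardstick. A separate question is whether the lower figure, 7, is covered throughout the stated SD range once the planned attrition is applied.

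**Working it through.** **Inputs (SAP, Power Analysis):** SD 16–20; two-sided alpha .05; 80% power; 110 per arm after 15% loss (130 × 0.85 = 110.5) or 130 per arm; equal allocation.

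**Step 1. Try to reproduce the stated range.** For a two-sample Wald test the detectable difference is SD × (1.960 + 0.842) × √(2/n). SD 16–20 is read here as the SD of the analysed outcome.

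| n per arm | detectable d | SD 16 | SD 18 | SD 20 |
|---|---|---|---|---|
| 110 | 0.378 | 6.04 | 6.80 | 7.56 |
| 130 | 0.347 | 5.56 | 6.25 | 6.95 |

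The 7 is recoverable (SD 20, 130 per arm: 6.95). The 15 is not.

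**Step 2. Compare the points with the stated d.** 0.4 × 16 = 6.4 and 0.4 × 20 = 8.0. The stated d therefore corresponds to 6.4–8.0 points. Power for d = 0.4 is Φ(0.4/√(2/n) − 1.960), which is 84% at 110 per arm and 90% at 130. The d statement is sound.

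**Step 3. Lower end.** Power for 7 points is Φ(7/(SD × √(2/n)) − 1.960).

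| n per arm | SD 16 | SD 18 | SD 20 |
|---|---|---|---|
| 110 | 90.1% | 82.2% | 73.8% |
| 130 | 94.2% | 88.0% | 80.6% |

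At 110 per arm, 80% holds up to SD = 7/0.3778 = 18.5.

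**Step 4. Upper end.** At 110 per arm, 15 points has over 99.9% power at SD 16 and at SD 20. It would need only 18 (SD 16) to 28 (SD 20) per arm for 80%. For 15 to be the 80% limit, the SD would have to be 15/0.3778 = 39.7 at 110 per arm, or 15/0.3475 = 43.2 at 130.

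**Step 5. Does a change-score reading rescue 15?** If SD 16–20 is per visit and change scores are compared, the SD is multiplied by √(2(1 − r)), where r is the correlation between baseline and week 8. The documents give no r, so these values are assumptions (110 per arm):

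| assumed r | SD 16 | SD 20 |
|---|---|---|
| 0 | 8.55 | 10.68 |
| 0.3 | 7.15 | 8.94 |
| 0.5 | 6.04 | 7.56 |

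A limit of 15 at SD 20 needs r = 1 − (15/7.556)²/2 = −0.97, which is not credible for repeated scores on one scale. Adjusting for baseline instead multiplies the SD by √(1 − r²), which can only lower the 6.0–7.6 limit.

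**The case against.** The strongest reply is that 7–15 was never a detection limit. The sentence speaks of a meaningful effect and of a d of 0.4 or more, which fits a span of effects worth finding, each with at least 80% power. With 130 per arm that is true throughout: the worst case, 7 points at SD 20, has 80.6%. This reading is fair and the fix allows for it. It does not fully hold in the SAP's own attrition case, where 7 points at SD 20 has 74% power. Keeping all 130 in the model does not settle that, because participants without a week-8 CAPS-5 add little information on change. The reading also leaves 15 without a source.

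Three further points on the other side stand.

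- A reader might infer that the whole range is wrong. It is not: 7 lies inside 6.0–7.6 and is recovered at 130 per arm.
- A reader might infer that 15 cannot be obtained on any reading. That goes too far. About 15.1 points does arise for a single-site change-score comparison (55 per arm, r = 0, SD 20), or for a treatment-by-subgroup interaction at SD 20 (2 × 7.56). The SAP describes neither as the basis of its power statement, so the conclusion is limited to the main comparison.
- The consequence is small. The upper end errs on the conservative side, the SAP goes on to use d = 0.4, the Continuing Review Form has superseded the inputs, and it reports that only data analysis remains.

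**Conclusion.** The point holds as a correction to a stated figure. For the main comparison, if SD 16–20 is the SD of the analysed outcome, the stated inputs give 6.0–7.6 points at 110 per arm, or 5.6–7.0 at 130. The 15 is about twice the largest of these (15/7.56 = 1.98). It also exceeds the 10.7 points reached under a per-visit reading with zero correlation. The 7 has 80% power at 110 per arm only up to SD 18.5.

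It would be tempting to conclude that the trial is underpowered. The documents do not support that: d = 0.4 has 84% power at 110 per arm, and overstating a detection limit understates the trial's sensitivity. The one real shortfall is for 7 points at SD above 18.5 with 110 per arm, and the later observed SD of about 11, whatever it denotes, is well below the assumed range.

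The result rests on the normal approximation, which matches the stated Wald test (a t-based calculation gives d = 0.379 at 110 per arm). The figures in points depend on what the SD denotes, which the SAP leaves open.

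**What to change.** In the SAP's Power Analysis, in this order:

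1. State whether SD 16–20 is the SD of the analysed outcome (change) or a per-visit SD.
2. Replace the 7–15 point range with the matching detectable difference. If it is the analysed-outcome SD, this is 6.0–7.6 points with 110 per arm (5.6–7.0 with 130). If it is per visit and change scores are compared, multiply those values by √(2(1 − r)) and state r.
3. Keep the statement that d of 0.4 or more is detectable.
4. If 7–15 was meant as a range of clinically meaningful effects, label it so, give its source, and keep it apart from the detectable difference. Note there that 7 points at SD 20 has 74% power with 110 per arm.

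In the report, say that the Continuing Review Form supersedes these inputs (SD about 11; 114 and 118 randomized). Define that SD before giving an updated detectable difference.

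Cost: wording in one SAP paragraph and in the report. No participant, analysis or estimate changes.

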**Table of Measures**

Measure	Construct	0 wk	8 wk	16 wk	24 wk
Blessed Orientation Memory Concentration	Cognitive Impairment	X			
Demographics & Military Background	Demo & Military Service	X			
Columbia-SSRS	Suicidal Ideation	X	X	X	X
Alcohol Use Identification Test (AUDIT)	Alcohol Use	X	X	X	X
Drug Abuse Screening Test (DAST)	Drug Abuse	X	X	X	X
Clinician Administered PTSD Scale-5 (CAPS-5)	PTSD (interview)	X	X		
VA Administrative Data	Treatment Engagement	X			X
Client Satisfaction Questionnaire (CSQ)	Treatment Satisfaction		X		
Patient Feedback Interviews	Patient Feedback		X		
Coping Self-Efficacy Scale	Coping Self-Efficacy	X	X	X	X
Patient Health Questionnaire-9 (PHQ-9)	Depression	X	X	X	X
WHO QOL-BREF	Quality of Life	X	X	X	X
PTSD Checklist-Specific-5 (PCL-5)	PTSD (self-report)	X	X	X	X

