## Method of Randomization

Both sites will have separate randomization schemes to allow simultaneous randomization at each site. Participants will be randomized in equal proportions to conditions. Randomization schemes will be created in a password protected excel files and local study coordinators will be able to access these files to determine the randomization outcome for each participant.

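### The site term planned for Aim 1 does almost nothing to the tested contrast; adding site-by-week would make the primary test site-adjusted, a small gain in efficiency

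*SAP*

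**What the plan says.** Under Method of Randomization the SAP states "Both sites will have separate randomization schemes to allow simultaneous randomization at each site" and "Participants will be randomized in equal proportions to conditions". No blocking is named.

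Under Data Analysis, the Aim 1 target is given as "we will measure the impact of CS PTSD Coach on change in CAPS-5 score at 8 weeks". On structure: "The mixed effects model will include a subject-specific random effect to account for the correlation of CAPS-5 score within a person over time". On inclusion: "As all participants will have a baseline score, they all will be included in the model, adhering to the ITT principle". On site: "because randomization is stratified by site, site will be included as a fixed effect in our model".

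The Table of Measures schedules CAPS-5 at weeks 0 and 8 only. The Aim 1 text names no time, condition-by-time or site-by-time term and does not say whether the arms share a baseline mean. Product terms of time and condition are written out only for the PCL trajectory model among the exploratory aims. Depression and quality of life are to be analysed in a way similar to Aim 1.

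**The concern.** The reason given for including site is the stratified randomisation, so a reader will take the primary comparison to be site-adjusted. Whether it is depends on what the term can reach. A participant's site is the same at both visits, while the tested quantity is the arm difference in within-person change. A term that adds the same constant to both scores has nothing to say about their difference.

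Two things are at stake. If the sites differ in mean change, that variation stays in the error term of the primary test. If the arms happen to be unevenly split within a site, the resulting shift stays in the estimate. Some site difference is plausible, because existing local primary care mental health providers deliver care in both arms and the sites contributed unequal numbers, but the documents give no figure for it.

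**Working it through.** **1. The model implied.** CAPS-5 has two visits, participants without week 8 stay in through their baseline score, and correlation over time is handled by a subject effect. Baseline is therefore an outcome row and the effect on change is condition-by-week. This is inferred; the SAP does not write it.

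**2. Algebra.** For participant i:

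- Baseline: a + b·arm + g·site + u + e0
- Week 8: a + b·arm + g·site + w + d·arm + u + e1
- Difference: w + d·arm + (e1 − e0)

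The site effect g has gone. If site-by-week (h·site at week 8) is added, the difference becomes w + d·arm + h·site + (e1 − e0), and d is adjusted for site.

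**3. Numerical check.** Random-intercept REML fits to simulated data: N = 234 split 164/70, SD 11, correlation 0.5 (assumed).

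- Complete data, free baseline means: adding the site main effect changed the estimate by at most 2e-14 points and the SE by under 1e-7 in relative terms.
- 15% or site-dependent dropout (200 runs per setting): the estimate moved 0.02 to 0.03 points on average, at most 0.20, against an SE of about 1.4 to 1.6. The SE moved by under 0.5%.
- Common baseline mean, complete data: the estimate moved 0.07 points on average and at most 0.47 with simple 1:1 assignment, and at most 0.09 with arms balanced within site.
- Type I error with complete data, simple assignment and no site difference in change (1,500 runs): 4.5% with or without the main effect, 4.3% with site-by-week.

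**4. Cost of leaving site-by-week out.** SE ratio = √(1 + p(1 − p)D² / Var(change)).

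- p = 70/234 = 0.299, from the Protocol's Continuing Review Form, item 1a (70 and 164 eligible for randomisation). So p(1 − p) = 0.2097.
- Var(change) = 2 × SD² × (1 − ρ) = 2 × 11² × 0.5 = 121. The SD of about 11 is from the same item; ρ = 0.5 is assumed.
- D, the site difference in mean change, is assumed.
- Power is Φ(2.802/ratio − 1.960), starting from a nominal 80%.

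| D (points) | Variance ratio | SE inflation | Power |
|---|---|---|---|
| 0 | 1 | 0% | 80% |
| 2 | 1 + 0.2097 × 4/121 = 1.007 | 0.3% | 79.7% |
| 3 | 1 + 0.2097 × 9/121 = 1.016 | 0.8% | 79.4% |
| 5 | 1 + 0.2097 × 25/121 = 1.043 | 2.1% | 78.3% |
| 8 | 1 + 0.2097 × 64/121 = 1.111 | 5.4% | 75.7% |

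Varying the inputs (SD 11 to 16, ρ 0.5 to 0.7, D 2 to 6) gives 0.2% to 5.1%. An SD of change of 9 with D = 8 gives 8.0%.

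**5. Chance imbalance, for illustration.** With 117 per arm, Palo Alto split 40/30 and D = 5, the unadjusted estimate shifts by 5 × (40 − 30)/117 = 0.43 points. The SE is 11 × √(2/117) = 1.44. The documents report no such imbalance.

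**6. The plan's own power figure.** With 110 per arm and d = 0.4, power is Φ(0.4 × √(110/2) − 1.960) = Φ(1.007) = 84.3%, so the stated 80% is met with room to spare. It does not depend on how site is handled.

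**The case against.** **The model is inferred.** Calling site a fixed effect may only distinguish it from the subject random effect and need not exclude site-by-week. This stands as a limit on certainty. But no site-by-week term is named, and the wording as it is leaves the adjustment to the analyst.

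**A reader might infer that the site term cannot affect the primary test at all.** The documents do not support that. The SAP expects 15% attrition and keeps those participants, and then the estimate moves slightly. It also moves under a common-baseline model, which the SAP does not exclude.

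**A reader might infer that the primary test ignores the stratification and is biased or invalid.** That is not supported either. Allocation is 1:1 within each site, so the estimate is unbiased over randomisation. Any error in the SE is in the conservative direction, and simulated type I error was close to nominal.

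**The size rests on assumed site differences.** This stands. At SD 11, the SAP's d = 0.4 is 4.4 points, so the 5- and 8-point rows suppose that the sites differ by more than the treatment effect sought. The Continuing Review Form also reports 114 + 118 = 232 randomised against a revised minimum of 2 × 95 = 190, a 22% margin that exceeds the 11% variance inflation at 8 points.

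**It is late to change the model.** The same form shows enrolment closed and only analysis remaining. But it also says that data are still being prepared and that there are no interim findings.

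**Conclusion.** The point holds as a minor matter of efficiency and specification. On the natural reading of Aim 1, the site term does not do the job for which the SAP includes it: its effect on the tested contrast is nil with complete data and negligible with the expected attrition. The price is an SE about 0.3% to 5% too wide, or under 1 to about 4 points of power, if mean change differs by 2 to 8 points between sites and the SD of change is near 11. Chance site imbalance also stays unadjusted. If the sites do not differ in change, nothing is lost. The conclusion rests on free baseline means and a condition-by-week test, which the SAP implies but does not state, and on an assumed correlation and assumed site differences.

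**What to change.** In the Aim 1 paragraph, list the fixed effects as condition, week, condition-by-week, site and site-by-week, with the subject random effect as planned, and keep every participant with a baseline score. State whether baseline means are free or common. Use the same site and site-by-week terms for PHQ-9 and WHOQOL-BREF, with one site-by-week term per follow-up visit modelled (three if weeks 8, 16 and 24 all enter).

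A week-8-only model with site as a covariate is not an equivalent substitute. It targets the week-8 score, or a baseline-adjusted one, rather than change, and it drops participants without week 8, whom the SAP keeps.

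The cost is one extra parameter for CAPS-5, no new data, and a dated amendment made before the model is fitted, so that the form of site adjustment is not chosen after results are seen. Where the sites did not differ in change, adding site-by-week raised the simulated SE by about 0.2% on average under simple assignment and 0.01% with arms balanced within site (complete data).
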